#### 4.5.3 Data collection

The primary mode of data collection for all the outcome measures will be technology mediated (see Figure 3). The check-in sessions and qualitative interviews (process evaluation only) will be conducted via an internet-based service (e.g. Zoom, MS Teams) or telephone platform by a member of the research team. The questionnaire outcome measures will be collected via the UCL online Qualtrics survey platform and then uploaded onto the UCL secure Data Safe Haven data management platform by a member of the research team. Check-in session documentation forms will be completed digitally during the check-in sessions by the research ream uploaded onto the UCL secure Data Safe Haven data management platform by a research team member. Analytics will be collected via the intervention web-based platform using a custom analytics dashboard built into the website and resulting data will be uploaded to the UCL Data Safe Haven by a member of the research team. Assessments will be done at baseline (T0), ~9 weeks after baseline (T1), and 6 months after baseline (follow-up, T2). Demographic data will be collected at baseline (e.g., age, gender, ethnicity, genetic risk status, education, occupation).

collection pathways and data management stipulations

Whilst every effort will be made to follow-up participants as close as possible to the defined time points this may vary e.g. due to the different speeds at which participants choose to move through the intervention. Date of data collection will be recorded.

### 4.5.4 Data analysis

Primary analysis will be conducted on an Intention To Treat (ITT) basis, blinded to treatment allocation. The primary assessment for effectiveness of the intervention will be adjusted estimates of the scores on the WEMWBS (14 item) scale between the intervention and Treatment As Usual (TAU) groups assessed at the 9-week follow up.

A linear mixed effects model adjusting for baseline scores, and other stratification variables (i.e., diagnosis, at-risk group type and gender) will be fitted for the scores on the WEMWBS at both the 9 weeks and 6 months follow ups. Similar models will be fitted for all the continuous secondary outcomes. All estimates of effect will be presented together with 95% confidence intervals. A sensitivity analysis will be conducted to assess the impact of the number of times the intervention is accessed

The aim is to minimise missing data; however, predictors of missingness will be investigated using regression models and any predictors found will be considered for inclusion in the models. Multiple imputation will be employed to address missing scores where appropriate. Analysis of complete case data will be completed as a sensitivity analysis to establish the sensitivity of the treatment effect estimates to the missing data.

A Statistical Analysis Plan (SAP) will be written and signed off before completion of data collection. The independent committees (i.e., TSC & DMEC) will have the opportunity to comment on the SAP. If any deviations from the planned statistical analyses are required these will be documented in the end of trial statistical analysis reports

### 4.6 Internal pilot study [WS1b]

#### 4.6.1. Internal pilot outcomes

- Progression criteria will be measured at 9 months (full study is 30 months from first participant recruited, with a projected recruitment of ~3-6 participants per month (in the first 24 months).
- 'Stop' [stop the trial], 'Review '[with adaptation to trial process], 'Go' [without adaptation] criteria thresholds are based on levels allowing completion of the trial within 30 months.

4.6.1. Internal pilot criteria:

- 1. Recruitment ('Stop'/'Review'/'Go' based on modelling non-linear recruitment scenarios):
  - Go=30 participants recruited
  - Review=15+ recruited
  - Stop=<15 recruited

- 2. Intervention attendance (i.e. check-in videoconference sessions):
  - Go=70%+ videoconference sessions attended
  - Review=60-69% attended
  - Stop=<60% attended
- 3. Intervention attendance (i.e. the number of participants who have logged in and used the system more than once):
  - Go=60%+ online content accessed
  - Review=40-59% online content accessed
  - Stop=<40% online content accessed

We will have limited data on retention and primary outcome completion at 9 months but will keep under continuous review. In relation to these, we will only stop the trial after the pilot if there is no outcome data or no one is retained at 9 months.

### 4.7 Process evaluation [WS2]

The process evaluation will run alongside the trial and will apply mixed-methods (quantitative questionnaires (e.g. the SUS), semi-structured interviews, and analysis of data from the online platform). It will be conducted in line with established guidance frameworks (Moore et al., 2015; O'Cathain et al., 2019). It will examine throughout the intervention period how participants engage with and adhere to particular aspects of 'IWARF' (e.g. most/least frequently visited pages, the most 'popular' modules/sessions).

Change mechanisms will be investigated by exploring the barriers, facilitators and contextual factors which influence the uptake and implementation of 'IWARF' (e.g. the at-risk genetic status of participants). The extent to which 'IWARF' may have changed behaviours beyond the intervention (e.g. mindfulness practice, values-guided action) will be explored. The usability of the website will be evaluated with the System Usability Scale (SUS; Brooke, 1996).

#### 4.7.1 Quantitative data collection (N = 59)

A System Usability Scale (SUS) will be administered to the IWARF intervention group immediately post-intervention as part of their Qualtrics battery of outcome measures. This 10-item scale will quantitatively evaluate the overall usability of the 'IWARF' platform. Each item is a statement (e.g. "I thought 'IWARF' was easy to use") and responses given on a 5-point Likert scale 0 (strongly agree) to 4 (strongly disagree). Total scores range from 0 to 40 which are then converted to 0-100 and normalised to produce a percentile ranking. The SUS is easy to administer, reliable and valid and effectively differentiates between usable and unusable systems. We will also collect data from the online platform regarding usability (e.g. frequency and length of use, which modules/ activities / pages users most frequently visit;

average length of time spent on each module / lesson / page per user; from tablet or PC). The number of contacts with the facilitator will also be recorded.

### 4.7.2 Qualitative data collection

Semi-structured interviews will be undertaken using an internet-based service (e.g. Zoom, MS Teams) or telephone, with a sub-sample of the intervention participants. These will be recorded and professionally transcribed. The topic guides will be guided by the process evaluation parameters described in recognised frameworks (Moore et al., 2015; O'Cathain et al., 2019) and drawing upon theoretical models such as Normalisation Process Theory (NPT; Murray et al., 2010) They will be developed in partnership with the PPI group and our collaborators. Regular meetings will be held with the research team to identify any new questions which arise from emerging themes. The content of any contact with the facilitator between check-in sessions will also be recorded (e.g. questions about the intervention, any requests for troubleshooting).

### 4.8 Health Economics

Health and social care resource use, including primary care, outpatient appointments, support groups as well as impacts on productivity and activities of daily living, will be measured with a participant reported resource use measure that has been developed for this population. An internal pilot will be conducted to assess the feasibility and acceptability of the resource use measure in the first 2 to 3 months of the trial (assessing to the first 15 participants responses). If completion rates indicate the resource use measure is not acceptable, edits will be made at this point and the IWARF PPI group will be asked for feedback on items where changes have been made.

Resource use will be translated into costs using published unit costs for the cost year for the evaluation (NHS reference costs (https://www.england.nhs.uk/publication/2021-22-national-cost-collection-data-publication/), PSSRU (Jones et al., 2023), BNF (https://www.nice.org.uk/bnf-uk-only)). Development costs, staff inputs, material and equipment associated with the IWARF intervention will be elicited from structured interviews with the trial team, finance staff and clinical sites as required.

Data will be summarized by mean and SD if data are normal, or median and IQR if data are skewed. The economic analyses will include the intent to treat population as for the statistical analysis. Data will be assessed for missingness, and if the assumption of missing at random can be made, then multiple imputation will be used if the number of cases lost due to incomplete information exceeds 10%. Imputed datasets will be combined using Rubin's rules before undertaking analyses. Sensitivity analyses will be performed to examine departures from the missing at random assumption in the imputation models.

A within-trial health economic analysis will be conducted based on the trial follow- up period of 6 months. Patient pathways will be developed with input from the research team given the limited published evidence available for this population. Net incremental costs and outcomes will be computed using the area under the curve method. Costs and outcomes will not be discounted as the within-trial time horizon is less than 12 months. A range of health economic analyses will be presented to inform comprehensive assessment of cost-effectiveness for decision makers. The primary analysis will be a cost-utility analysis. The net monetary benefit will be used to summarise QALY benefits against willingness to pay thresholds (NICE, 2013). Sufficient capability will be assessed using the ICECAP-A, which is a broader wellbeing/capability measure, cost-effectiveness will be assess against the threshold for a year of sufficient capability well-being (Kinghorn and Afentou 2021). A cost-effectiveness analysis estimating the incremental costs of achieving clinically significant improvement in atrisk mental wellbeing as this analysis will be relevant to health care professionals, healthcare decision makers and service users; however, interpretation of this ICER will be limited as there is no threshold to determine what represents good value for money A range of sensitivity analyses will be conducted to address the impact of uncertainty on our findings.

The base case analysis will be conducted from a societal perspective including impact on ability to work, a further analysis with a UK NHS and personal social services perspective will be conducted to allow comparison with other published economic evaluations.

A health economic analysis plan will be written following good practice with reporting of the health economic analysis conforming to the Consolidated Health Economic Evaluation Reporting Standards (Husereau et al., 2022).

# 5. ASSESSMENT OF SAFETY

## 5.1 Definitions

Adverse Event (AE): Any untoward medical occurrence in either a trial study participant which does not necessarily have a causal relationship with the intervention.

Serious Adverse Event (SAE): Any adverse event that a) Results in death; (b) Is life threatening; (c) Requires hospitalisation or prolongation of existing hospitalisation; (d) Results in persistent or significant disability or incapacity; or (e) Is otherwise considered medically significant by the investigator. Pre-existing conditions do not qualify as adverse events unless they worsen over the course of the trial.

## 5.2 Collecting, recording and reporting of adverse events

Assessment of AEs and SAEs brought to the attention of the research team will be undertaken and overseen by an independent Data Monitoring & Ethics Committee (DMEC), who will report to the Trial Steering Committee (TSC). The DMEC will be able to advise on changes to the conduct of the trial via recommendations to the TSC and will also receive regular safety reports from the team.

The adverse event reporting period for the trial begins as soon as participants consent to take part and one month after their final data collection ends. All adverse event data the research team are made aware of will be collected and recorded in line with University College London's Research Ethics Committee stipulations on Adverse Event Reporting – Serious and Non-Serious (as outlined in the approval letter dated 10/01/2024). Reporting of SAEs will also form part of the trial delegation log and be covered in training for research team members

involved in data collection. The documentation for SAE and AE reporting is outlined in the trial folder on the Data Safe Haven.

Reports will be sent to the Trial Management Team, the Research Ethics Committee, DMEC and TSC within the required timelines from the approval letter (immediately upon notification of an SAE, and within ten days of the AE being brought to the research team's attention). Other adverse events will be noted in the same log as the SAEs and a monthly report will be compiled by the Trial Lead (EH) for review by the Trial Management Team.

Safety analysis will be pre-specified analyses in the statistical plan led by NWORTH and can be represented graphically e.g. as volcano plots or in the usual tabular format. The former plots all SAEs and provides a visual representation of outliers. This method is preferred to inferential analysis, as they would be under-powered. Using graphical methods will allow the DMEC to identify any potential safety signals and these will be reported to the TSC.

A copy of the AE and SAE CRF will be stored at the recruiting site in the ISF, and those signed by the Chief Investigator stored in the Trial Master File (TMF).

Given the nature of the intervention, we do not feel there are serious safety concerns for the participants. However, we will be collecting data on psychological distress (e.g. anxiety and depression). This data will be available to the DMEC during the course of the trial.

If someone living at-risk of a familial dementia becomes symptomatic with dementia during the course of the intervention, we will discuss with them on a case by case basis regarding continuing with the trial (e.g. completing measures, accessing the intervention). Participants are always able to withdraw at any point for any reason and will be reminded of this. We will ensure we record their change in health status in the relevant trial documentation (e.g. a file note) and it has been confirmed by our trial statistician that this change in status will pose no issue for analysis.

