# 4. TRIAL PROCEDURES

### 4.1 Planned intervention

Following consent, baseline measures and randomisation, the intervention group will receive the Improving wellbeing Associated with Rare Familial dementias (IWARF) programme, an 8week intervention comprising 8 online modules with additional psychoeducational videos. Modules cover issues identified as important in intervention development (e.g., rumination about risk or positive genetic status; uncertainty; making the most of life at-risk; isolation). Issues known to be pertinent to at-risk individuals are addressed using a mixture of materials (e.g. videos and independent activities) most drawing on Acceptance and Commitment Therapy (e.g., using mindfulness-based acceptance techniques to manage rumination; see Appendix 1. 'IWARF' logic model for summary). A brief introductory video shows participants how to use the intervention and to explain the different features. Participants complete the modules that correspond to their needs, at their own pace within ~8 weeks. Up to 3 total interactions between facilitators and participants will be offered to support participants' engagement with the programme via virtual check-ins. These check-in sessions will occur at intervention-beginning, middle and end (facilitated by a Research Assistant or Research Fellow who is trained/supervised by [name], [name] and [name]). Once participants have completed the trial they will be granted ongoing access to the intervention materials.

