## 4.2 Comparison group

Following consent, baseline measure data collection and randomisation, the waiting list control group will receive explicit signposting to TAU participants may already be receiving (e.g., Rare Dementia Support website ). This a wait list study where the control group will be given access to the intervention's online materials after the individuals' last point of data collection.

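### Adverse events are recorded only when staff hear of them, and the intervention arm has more contact with staff, so the between-arm safety display is at risk of ascertainment bias

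*Protocol*

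**What the plan says.** **Collection.** Protocol Section 5.2 makes collection depend on awareness: "All adverse event data the research team are made aware of will be collected and recorded". The oversight sentence is worded the same way: "Assessment of AEs and SAEs brought to the attention of the research team will be undertaken". Table 1, the schedule of measures, has no adverse-event item at any time point.

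**Contact in the intervention arm.** Section 4.1 states: "Up to 3 total interactions between facilitators and participants will be offered". These sessions are "facilitated by a Research Assistant or Research Fellow". Section 4.7.2 adds that the content of facilitator contact between check-ins is recorded, and that a sub-sample of intervention participants is interviewed. Section 7.1 requires a form after each interview noting any distress or cause for concern.

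**Contact in the control arm.** Section 4.2 gives controls signposting to usual support. Section 4.5.3 collects questionnaires online in both arms.

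**Reporting period.** Section 5.2 says that it "begins as soon as participants consent to take part and one month after their final data collection ends". Section 4.2 says that the "control group will be given access to the intervention's online materials after the individuals' last point of data collection".

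**Use.** Section 5.2 plans graphical or tabular safety displays, with volcano plots as the example, so that the DMEC can see possible signals. It leaves the detail to the statistical plan.

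**The concern.** When events are logged only if someone mentions them, the count depends on how often participants speak to staff as well as on how often events occur. Here the number of conversations differs by arm by design. A participant in the intervention arm may mention a hospital visit at a check-in. A control with the same event may fill in two online surveys that never ask about it.

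The DMEC would be reading these data for signals. With 59 per arm, a few extra recorded events could look like an excess under the intervention when only the noticing differs. The staff who hear of events do not offset this: Section 3.4 lists the Trial Lead and Research Assistants as unblinded, and Section 5.2 has the Trial Lead compile the monthly report.

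The statistical analysis plan can choose which recorded events to display. It cannot recover control-arm events that nobody asked about. The collection method is fixed in the protocol, so it has to be changed there.

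**Working it through.** The protocol gives no adverse-event figure to reproduce. The check sets the routes to notice side by side, then adds two illustrations.

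**Step 1: routes by which an event can reach the team**

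| Route (protocol section) | Intervention | Control | Stated to be an adverse-event source? |
|---|---|---|---|
| Online surveys at T1 and T2 (Table 1, 4.5.3) | yes | yes | no adverse-event item |
| Automatic alert on PHQ-9 suicidality item or severe anxiety/depression (7.1) | T0, T1, T2 | T0, T1, T2 | no |
| AR-RUM resource-use measure (4.5.2, 4.8) | T0, T1, T2 | T0, T1, T2 | no |
| Live check-ins (4.1) | up to 3 | none described | no, but run by research staff |
| Facilitator contact between check-ins (4.7.2) | content recorded | none described | no |
| Process-evaluation interview (4.7.2, 7.1) | sub-sample | none under 4.7.2 | no |
| Spontaneous report | possible | possible | yes, by awareness |

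The first three routes and the last are the same in both arms. The three in between are open to the intervention arm only. One caveat: Section 3.2.2 speaks of first inviting all participants to interview, whereas 4.7.2 confines interviews to intervention participants. The table follows 4.7.2. The check-ins and between-session contact do not depend on it.

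**Step 2: illustration of size (assumed inputs)**

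Assume equal true event rates, and a chance q that an event is noticed at each occasion. Controls have 2 post-baseline occasions (T1, T2). The intervention arm has up to 2 + 3 = 5. The apparent ratio is

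R(q) = [1 − (1 − q)^5] / [1 − (1 − q)^2]

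| q | Intervention, 1 − (1 − q)^5 | Control, 1 − (1 − q)^2 | R |
|---|---|---|---|
| 0.1 | 0.410 | 0.190 | 2.16 |
| 0.2 | 0.672 | 0.360 | 1.87 |
| 0.3 | 0.832 | 0.510 | 1.63 |
| 0.5 | 0.969 | 0.750 | 1.29 |
| 0.8 | 1.000 | 0.960 | 1.04 |

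The protocol gives no q. The model lets every occasion catch every event, which puts it at the upper end. Section 4.5 places T1 about a week after the third check-in, so an event that starts later has the same survey occasions in both arms and contributes a ratio of 1. Against that, the model omits interviews and between-session contact, and it gives a survey without an adverse-event question the same chance as a conversation. It shows that the effect could be anything from negligible to large. It is not an estimate.

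**Step 3: the reporting period**

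The sentence has a start but no grammatical end. Its most natural reading is that reporting stops one month after final data collection. With T2 at 6 months, that gives 6 + 1 = 7 months, of which 1/7 = 14% follows T2. For controls without attrition this is 59 × 1 = 59 of 59 × 7 = 413 person-months, in which they may have the online materials. This is a share of time and not of events: no contact is scheduled after T2, so few events may be recorded then.

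**The case against.** **Distress is detected equally.** Section 7.1 names distress as the main ethical concern. The survey alert works the same way in both arms at T0, T1 and T2, with staff follow-up within 72 hours, and Section 5.2 makes the anxiety and depression data available to the DMEC. This stands, and it narrows the point. However, Section 5.1 defines an adverse event as any untoward medical occurrence, and the alert sees only distress at survey times. AR-RUM asks both arms about health-care use, but it is described as an economic measure.

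**Check-ins are not adverse-event interviews.** Their stated purpose is engagement, and all fall in roughly the first 8 weeks. This also stands and limits the size. It does not remove the difference, because Section 5.2 requires staff to record whatever they become aware of.

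**Unseen documents may cover it.** Section 5.2 refers to the ethics approval letter and to AE and SAE forms, which could specify how events are elicited. If they prescribe the same enquiry in both arms, the protocol should say so. As written, it describes passive collection.

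**No formal test is planned.** True, and Section 5.2 does not say in words that displays are by arm, though a volcano plot is a between-arm display. Unequal capture distorts a picture as much as a test.

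**Stronger readings to avoid.** A reader might infer that the comparison is known to be biased against the intervention by a stated factor. The documents do not support this: no detection rates are given. The net direction is open too. For example, if controls stay more distressed, they could trigger more alerts and so more staff contact. A reader might also infer that events after T2 will be counted under control and mask a real signal. Section 5.2 sets a reporting period and does not say how those events are tabulated. Section 4.2 gives controls online materials only, with no check-ins described, and Section 4.1 gives the intervention arm ongoing access as well. Nor are the two effects inseparable, since onset dates and the route of notice would separate them.

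**Conclusion.** The point holds as a risk of unequal ascertainment by arm. It rests on three features of the protocol: passive recording, no scheduled adverse-event question, and live contact with research staff in one arm only. Distress at survey times is captured equally. Other events, including hospitalisations, are not protected in the same way.

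Neither the size nor the net direction can be derived from the documents. The ratios of 1.04 to 2.16 depend entirely on the assumed chance of notice per contact and show only that the effect need not be small. The primary outcome is unaffected. What is weakened is how far the DMEC can read a difference, or the lack of one, in recorded events.

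The reporting-period wording is a secondary matter. The sentence needs correcting, and if the period does run a month past T2, the plan should say how events in that month are shown.

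**What to change.** 1. Add one identical adverse-event and hospitalisation question, with onset date, to the existing T1 and T2 Qualtrics surveys in both arms.
2. Add a field to the adverse-event record for how each event came to notice: survey, check-in or spontaneous. Interviews and between-session contact should be codable as well.
3. Base the between-arm tables and plots on survey-elicited events with onset from randomisation to T2. List events learned only by other routes separately, so that nothing is lost. Reporting of individual events stays as it is.
4. Rewrite the reporting-period sentence in Section 5.2 so that start and end are both explicit. If the end is one month after final data collection, list events after T2 separately, noting whether controls had the online materials by then.

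**Cost.** One survey item at two existing time points, one extra field, a tabulation rule and a protocol amendment. The main downside is more minor events to log. The survey-based display also covers only those who complete the surveys (about 0.8 × 59 = 47 per arm at the planned 20% attrition), which is a further reason to keep the full listing beside it.
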